#### **17.4 Patient Rights**

If the research subject suffers any physical injury as a result of their participation in this study, immediate medical treatment is available at the treating institution. Although no compensation is available, any injury as a result of his participation will be evaluated and treated in keeping with the benefits or care to which he is entitled under applicable regulations.

If the research subject has any questions regarding this research project, he may contact [name] or site investigator or coordinator or IRB. If he has any questions regarding his rights as an individual while participating in a research project at the Yale Cancer Center (YCC), he can contact one of the Research Administrators, Clinical Investigation Department, who will answer the research subject's questions or refer him to a member of the committee for the Protection of Human Subjects for further information. If the patient believes that he has been injured as a result of this project, he may call the legal office of YCC.

Participation in this research project is voluntary. A patient's refusal to participate will involve no penalty or loss of benefits to which he is entitled under applicable regulations. If he chooses to participate, he is free to ask questions or to withdraw from the project at any time. If he should decide to withdraw from the research project, he will notify the PI either directly or indirectly through the research nurse, to make sure the reasons for withdrawal are recorded and to ensure that everything is in order. A patient's withdrawal will involve no loss of benefits to which he is entitled.

The investigators may terminate the research subject's participation in this project for the following reasons: growth of cancer, intolerance of treatment, inability to comply with the protocol guidelines for treatment and follow-up, or if the patient chooses to stop protocol therapy, or at the specific request of MEI. Any new significant finding developed during the course of the research which may affect his willingness to participate further will be explained to the research subject.

### **18. EXPLORATORY STUDIES**

#### **18.1 KRAS mutation-associated circulating tumor DNA**

Activating mutations in the *KRAS* oncogene are present in over 90% of pancreatic adenocarcinomas, resulting in constitutive activation of signaling pathways that promote cell proliferation, transformation, and invasion. Single point mutations in codon-12 at G12 are most common, while codon-13 (G13D) or codon-61 (Q61L or Q61H) mutations are more infrequent.

Circulating tumor DNA (ctDNA) has emerged as a promising non-invasive biomarker that may correlate with treatment response and prognosis. At our institution, [name] has developed methods for quantitative detection of cancer-specific mutations in ctDNA from peripheral blood samples. Mutation hotspot regions of plasma DNA are amplified, and deep sequencing is used to quantify the rare DNA containing tumor-specific mutations. Given the high frequency of *KRAS* mutations in pancreatic tumors, we will collaborate with [name] to evaluate levels of *KRAS* mutation-associated circulating tumor DNA in BRPC patients enrolled on this study. Levels of *KRAS* mutated ctDNA will be correlated with radiographic and pathologic response to neoadjuvant therapy, onset of local and

systemic recurrences, and survival outcomes. Blood samples for ctDNA analysis will be collected at the following time points:

- At diagnosis (within 2 weeks prior to initiation of chemotherapy)
- After 8 cycles of mFOLFIRINOX (at the time of CT simulation)
- On the day of fraction 3 and fraction 5 of SBRT
- After SBRT (within 4 weeks prior to surgery)
- Day 1 of adjuvant mFOLFIRINOX (within 12 weeks of surgery)
- At completion of adjuvant mFOLFIRINOX
- At follow up every 3 months for 3 years, then every 6 months for 2 years, then annually until recurrence or death
- At the time of disease progression

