**2.3 Exploratory Objectives**

- 2.3.1 To prospectively assess quantitative *KRAS* mutation-associated circulating tumor DNA as a predictive marker of response to neoadjuvant therapy or a prognostic marker of outcomes.
- 2.3.2 To evaluate endoscopic ultrasound elastography measurements of tumor stiffness (change in strain ratio between the normal and tumor region before and after chemotherapy) as a predictor of outcomes.
- 2.3.3 To correlate response of CA19-9 to pre-operative therapy with outcomes.
- 2.3.4 To collect and bank serial serum and plasma specimens from subjects for future correlative biomarker studies.
- 2.3.5 To collect and bank tumor tissue from subjects prior to treatment (at the time of diagnostic EUS), after treatment with pre-operative FOLFIRINOX (at the time of fiducial placement for SBRT), and after SBRT (from the surgical specimen) for future correlative biomarker studies.

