**3. STUDY DESIGN****3.1 Description of Study**

This is a Phase II open-label study to determine the efficacy of neoadjuvant mFOLFIRINOX followed by SBRT in patients with borderline resectable pancreatic adenocarcinoma. Patients will undergo a diagnostic endoscopic ultrasound (EUS) with core biopsy (or FNA if biopsy is attempted and unsuccessful) demonstrating pancreatic adenocarcinoma. Baseline elastography will be measured at the time of EUS, though patients will continue on study if elastography is not feasible. Borderline resectable disease will be defined by NCCN criteria, and determined centrally by review of a diagnostic pancreas protocol CT scan and/or MRI scan with contrast by a dedicated surgical oncologist and radiologist.

Patients will receive 8 cycles of mFOLFIRINOX every 2 weeks. mFOLFIRINOX will be dosed as follows: Oxaliplatin 85 mg/m^2, followed by folinic acid 400 mg/m^2 infused over 120 minutes and irinotecan 135 mg/m^2 infused over 90 minutes, followed by 5-fluorouracil 300 mg/m^2 IV bolus, followed by 2,400 mg/m^2 continuous infusion for 46 hours. Levoleucovorin may be substituted for folinic acid at a dose of 200 mg/m^2 infused over 120 minutes.

Patients will undergo a re-staging pancreas protocol CT scan after cycle 3 and after cycle 7. Patients without evidence of distant progression will continue on study. Patients will receive an additional 8th cycle of mFOLFIRINOX while radiation planning is underway. EUS will be performed for placement of fiducials to guide radiation delivery. Elastography will be performed and a core biopsy will be obtained at the time of EUS for correlative studies (patients will continue on study if elastography and core biopsy is not feasible). Stereotactic body radiotherapy (SBRT) will be delivered to the primary tumor and any adjacent involved nodes to 33 Gy in 5 fractions over the course of 2 weeks, and within 4 weeks of chemotherapy. All patients will be maintained on proton pump inhibitors beginning with the first SBRT treatment and continuing for at least 6 months after completion of SBRT, or at least until surgery if undergoing resection. After SBRT, patients will undergo re-evaluation with a pancreas protocol CT scan. Those patients who are resectable will undergo surgical resection between 4-12 weeks after completion of SBRT. Tissue from the resection will be banked for correlative studies. Post-operatively, patients will

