## **6.2 Neoadjuvant SBRT**

Patients without evidence of distant progression will receive SBRT directed at the primary tumor. An 8th cycle of mFOLFIRINOX will be administered during planning for SBRT. All patients will be maintained on proton pump inhibitors beginning with the first SBRT treatment and continuing for at least 6 months after completion of SBRT, or until surgery if undergoing resection.

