### **6.2.2 Simulation**

CT simulation for radiation planning will be performed after the placement of fiducials. Patients will be NPO 3 hours prior to the scan, with the exception of oral contrast 30 minutes prior to the scan. Patients will be positioned supine in a custom vac-loc immobilization device. A dual phase (arterial and venous) IV contrast scan with 1.25mm slices will be obtained for target delineation. If the patient cannot tolerate IV contrast, the scan will be obtained without contrast and merged to diagnostic imaging (MRI, PET, and/or prior CT with contrast) for target delineation. A 4D-CT scan (with 2.5mm slice thickness) will then be obtained to characterize tumor motion with respiration. Abdominal compression will be applied for respiratory motion management, with the goal of decreasing motion of the fiducials to 5mm or less. The IV contrast and 4D scans will include from the carina to the iliac crests. Patients must begin SBRT within 3 weeks of the simulation scan.

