Surgical Resection M					

Long Term Follow-up PeriodN:			
Tests & Observations	Every 3 months (for the first three years after completing mFOLFIRINOX)	Every 6 months (three years after completing mFOLFIRINOX for the next two years)	Annual (five years after completing mFOLFIRINOX)
Scheduling Window (Days)	Every 3 months ±14 days	Every 6 months ±14 days	Annually ± 14 days
History	x	x	x
Physical Exam	x	x	x
Weight/BSA	x	x	x
Performance Status	x	x	x
Laboratory StudiesA:			
CBC, Diff, Platelets	x	x	x
Serum Chemistries B	x	x	x
CA 19-9, CEA	x	x	x
Research Blood Collection E	x	x	x

Follow-up PeriodN:		
Staging:	Every 6 months (first three years after completing mFOLFIRINOX)	Annually (three years after completing mFOLFIRINOX for two years)
Scheduling Window (Days)	Every 6 months ±14 days	Annually ±14 days
CT (or MRI) F	x	x

- A** Laboratory studies must be drawn within 24 hours of administration of drugs
- B** Serum chemistry panel will include serum creatinine, BUN, electrolytes (Na, K, Cl, Bicarb), AST/ALT, Alk Phos, Bili, and albumin
- C** PT/INR should be monitored weekly for those taking coumadin or warfarin
- D** For women of child-bearing potential only
- E** 3 purple top tubes (30 mls) at diagnosis, and 2 – 3 purple top tubes (20 – 30 mls) at each follow up time point, for cryopreservation of plasma and buffy coat
- F** CT should be performed using pancreatic protocol when possible. For patients who are unable to undergo CT, MRI may be used
- G** If elastography is not feasible, patients can remain on study
- H** At the time of diagnosis, core biopsies will be attempted with one specimen sent to pathology for diagnosis and a separate specimen to be banked for correlative studies. If core biopsies are not successful, a FNA is acceptable for diagnosis. At the time of EUS for fiducial placement, a core biopsy will be obtained and banked for correlative studies. Patients can continue on study if core biopsy is not feasible at the time of fiducial placement.
- I** At the time of CT simulation
- J** On the day of fraction 3 and fraction 5 of SBRT
- K** CT scan and plasma and serum samples will be done within 4 weeks prior to surgery
- L** Endoscopic ultrasound is optional if deemed necessary for surgical assessment

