## 18.3 Immunomodulatory Effect of SBRT

Pancreatic tumors are characterized by a dense desmoplastic stroma and infiltration of predominantly immunosuppressive leukocytes including tumor-associated macrophages (TAMs) and regulatory T cells with rare effector T-cells, which together promotes evasion of the immune system. While immune

checkpoint inhibitors have shown promising activity in melanoma, lung cancer, and other malignancies, responses in patients with advanced pancreatic cancer have been disappointing, likely in part due to the immunosuppressive pancreatic tumor microenvironment. Radiotherapy has both immune stimulatory and suppressive effects. Radiation triggers the release of tumor antigens, recruits effector T cells through induction of chemokines, and increases expression of co-stimulatory molecules and death receptors on tumor cells which enhances antitumor immunity. Radiation can also stimulate immunosuppressive leukocytes and induce expression of PD-L1. Recent reports have suggested that radiation and immune checkpoint inhibitors can act synergistically to promote anti-tumor immunity.

To better understand the immunomodulatory effect of stereotactic radiation on the pancreatic tumor and tumor microenvironment, we propose to characterize the tumor-infiltrating lymphocyte (TIL) population and expression level of PD-1 and PD-L1 in pancreatic tumors before and after stereotactic radiation. It is rare to have tissue available for analysis after SBRT, as SBRT is most often employed as a non-invasive treatment in place of surgery. Because SBRT will be performed pre-operatively in this study, core biopsies obtained at the time of fiducial placement prior to SBRT can be compared to surgical specimens in those patients who undergo successful resections after SBRT.

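### The pre-SBRT ctDNA draw is labelled as following eight cycles but tied to CT simulation, whose order relative to cycle 8 is not fixed, so a clean post-chemotherapy, pre-SBRT sample is not assured

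*Combined protocol and SAP*

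**What the plan says.** **Blood.** Section 18.1 lists a ctDNA sample "After 8 cycles of mFOLFIRINOX (at the time of CT simulation"). Footnote I of the Calendar of Assessments, attached to the pre-SBRT research blood, reads only "At the time of CT simulation" and sets no condition about cycle 8. The next samples are "On the day of fraction 3 and fraction 5 of SBRT". No sample is listed for fraction 1.

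**Cycle 8.** Section 3.1 gives an eighth "cycle of mFOLFIRINOX while radiation planning is underway". Section 6.2 likewise says that the eighth "cycle of mFOLFIRINOX will be administered during planning for SBRT".

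**Simulation.** Section 6.2.2 describes simulation as a radiation-planning step that follows fiducial placement, and adds: "Patients must begin SBRT within 3 weeks of the simulation scan".

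**Tissue and elastography.** Section 2.3.5 describes the second tissue sample as taken "after treatment with pre-operative FOLFIRINOX (at the time of fiducial placement for SBRT"). Section 18.2 places the second elastography at the same visit and also calls it post-FOLFIRINOX. Section 18.3, which aims to characterise the immunomodulatory effect of SBRT, says that "core biopsies obtained at the time of fiducial placement prior to SBRT can be compared to surgical specimens".

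**The concern.** Section 18.1 uses two anchors for one sample: completion of eight cycles, and the simulation visit. They agree only if simulation happens after cycle 8. Cycle 8 is deliberately overlapped with planning, and simulation is an early step of planning, so the two anchors can come apart.

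Where they do, samples carrying one label are taken at different points of chemotherapy in different patients. No later sample repairs this, because the next one is taken during radiation. A change from the simulation draw to fraction 3 or 5 could then include a chemotherapy cycle as well as SBRT.

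The same problem reaches the fiducial visit, which is earlier still. It matters most for Section 18.3, the one place where the plan sets out to describe an effect of SBRT itself. If cycle 8 falls between the biopsy and the first fraction, a change in PD-1, PD-L1, infiltrating lymphocytes or T-cell clonality cannot be credited to SBRT alone. Specimens not taken at the right time cannot be collected afterwards.

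**Working it through.** The plan gives no figure for this point, so the check is a calendar of what its windows permit.

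**Inputs from the documents**
- Cycle length 14 days; 5-FU infusion 46 hours (Section 6.1).
- SBRT starts at most 21 days after simulation (Section 6.2.2).
- SBRT is given within 4 weeks of chemotherapy (Section 3.1). No minimum gap is stated.
- Restaging CT after cycle 7 and within 4 weeks before SBRT (Section 8).
- 5 fractions of 6.6 Gy, 33 Gy in total (Section 6.2.3).

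**Assumptions.** Day 0 is cycle 8 day 1, so cycle 7 day 1 is day -14. The restaging CT falls between day -12 (end of the cycle 7 infusion) and day 0. Simulation follows that CT and comes at least a day before SBRT.

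**Simulation window.** If SBRT starts on day s, simulation may fall from day s - 21 to day s - 1, but not before the CT. With a CT no later than day 0, the 28-day CT limit gives s ≤ 28.

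| SBRT start (s) | Permitted simulation days | Before cycle 8 | Within its 14 days (days 0-13) | After its 14 days |
|---|---|---|---|---|
| 14 | -7 to 13 | -7 to -1 | 0 to 13 | none |
| 21 | 0 to 20 | none | 0 to 13 | 14 to 20 |
| 28 | 7 to 27 | none | 7 to 13 | 14 to 27 |

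Over all permitted starts, simulation can fall from about day -12 to day +27. The early extreme needs SBRT by day 9 (-12 + 21 = 9).

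**When is the label secure?**
- If after eight cycles means after the full 14 days, every permitted simulation day qualifies only when s - 21 ≥ 14, that is s ≥ 35. This is beyond day 28, so no permitted start date secures it.
- If it means after the eighth infusion has ended (about day 2), the condition is s - 21 ≥ 2, that is s ≥ 23. Starts on days 23 to 28 secure it and earlier starts do not.

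**Gap to SBRT and to the next sample**
- Longest simulation-to-SBRT interval: 21 / 14 = 1.5 cycle lengths.
- Share of neoadjuvant chemotherapy that may be missing at the draw: 1 / 8 = 12.5%.
- Dose delivered before fraction 3: 2 × 6.6 = 13.2 Gy, and 13.2 / 33 = 40%.

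**Biopsy and elastography.** Fiducials come before simulation (Section 6.2.2). If simulation precedes cycle 8, the fiducial visit does too. If simulation falls within or after cycle 8, the fiducial visit may still have come before it.

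**The case against.** **The order is open, not wrong.** No section puts simulation or fiducial placement before cycle 8. Section 3.1 narrates cycle 8 first and the fiducial EUS next; Sections 2.3.5, 18.1 and 18.2 all show an intent to sample after chemotherapy; and planning also includes contouring and dose work that follows simulation. This stands. A reader might infer that the plan has no clean pre-SBRT baseline, or that cycle 8 always follows the biopsy and elastography. The documents do not support either: the windows also permit a draw after the whole of cycle 8. What they lack is any provision that makes this happen.

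**Within cycle 8 is not before cycle 8.** The drugs are given at the start of the cycle, so a draw late in the 14 days follows all eight administrations. This is fair, and it narrows the set of patients for whom the label is plainly untrue.

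**No stated ctDNA aim isolates SBRT.** Sections 2.3.1 and 18.1 relate ctDNA to response to the whole neoadjuvant sequence, recurrence and survival. The diagnostic and pre-operative draws bracket that sequence regardless. This also stands: a mixed change from simulation to fraction 3 defeats no stated ctDNA objective. It does not answer the tissue point, because Section 18.3 is explicitly about SBRT.

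**The figures are not bias estimates.** Correct. The 21 days is a permitted maximum, 12.5% is one cycle in eight, and the 40% describes a sample intended to be on treatment. They show how far apart the anchors can lie, not how far any result would move.

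**CA 19-9.** A reader might assume that the pre-SBRT CA 19-9 shares the problem. It does not: the calendar places it in the general window of 4 weeks before radiation, without footnote I.

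**Conclusion.** The concern holds as a gap in assurance. The sections on cycle 8, simulation and the research draw do not fix the order, so a post-chemotherapy, pre-SBRT ctDNA sample is possible but not guaranteed. Its position relative to cycle 8 may vary between patients under one label. The biopsy and elastography may likewise precede cycle 8 although they are described as post-FOLFIRINOX. In those patients the Section 18.3 comparison reflects cycle 8 plus SBRT.

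How many patients would be affected cannot be computed, because the documents give no expected interval between cycle 8, simulation and SBRT. The day ranges rest on the assumptions listed with the calendar, mainly that the restaging CT is done by cycle 8 day 1.

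The consequence is limited. These analyses are exploratory, and Section 12 says that the study is not powered for them. The primary R0 endpoint and the two-stage design are unaffected. The change is still worth making, because it is nearly free and mistimed specimens cannot be replaced.

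**What to change.** 1. In Section 18.1 and footnote I, move the existing pre-SBRT research draw from CT simulation to the day of SBRT fraction 1, before treatment. The post-eight-cycle label is then true for every patient who receives all eight cycles.
2. Record the date and the number of mFOLFIRINOX cycles received at the draw, the fiducial-visit biopsy and the elastography. This is still needed after step 1, because the plan sets no minimum gap between chemotherapy and SBRT and some patients may receive fewer than eight cycles.
3. In Sections 2.3.5 and 18.2, describe the fiducial-visit biopsy and elastography by cycles actually received.
4. In Section 18.3, describe and analyse the paired tissue comparison as including any mFOLFIRINOX cycle given between biopsy and surgery, and report how many pairs have one.

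**Cost.** Wording in a few sections and one footnote, plus a date and a cycle count on the case report form. The number of tubes is unchanged, the patient already attends for fraction 1, and the treatment schedule does not change.

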#### **6.3 Surgery**

After completion of SBRT, patients will undergo re-evaluation for resection with a pancreas protocol CT scan, MRI if CT scan can not be tolerated, and PET or EUS if deemed necessary to determine resectability. Those patients who are determined to be potentially resectable will undergo a laparoscopy, followed by surgical resection within 4-12 weeks after completion of SBRT. For surgical resections occurring more than 12 weeks after SBRT, exceptions will be recorded and patients can remain on study with PI approval. Standard pathologic evaluation and staging will be performed.

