### Calendar of Assessments

Neoadjuvant mFOLFIRINOX:					
Tests & Observations	Screening			Day 1 of each cycle	Day 3, 4, or 5 of each cycle
	Within 14 days of starting study drug	Within 21 days of starting study drug	Within 42 days of starting study drug		
Scheduling Window (Days)				(±3)	(±3)
Surgical Evaluation			x		
History & Physical	x			x	
Height	x				
Weight/BSA	x			x	
Vital Signs	x			x	
Performance Status	x			x	
Toxicity Assessment	x			x	
Neulasta Q					x
Laboratory StudiesA:					
CBC, Diff, Platelets	x			x	
Serum Chemistries B	x			x	
PT/INR C	x				
CA 19-9, CEA	x				
Pregnancy Test D	x				
Research Blood Collection E	x				
Staging:					
CT (or MRI) F		x			
EUS (with elastography) G			x		
Neulasta					x
Tissue:					
Core Biopsy H			x		

Neoadjuvant SBRT and Pre-Operative Evaluation:			
Tests & Observations	Pre-SBRT (within 4 weeks prior to RT)	Weekly During SBRT	Pre-operative (within 4 weeks prior to surgery)
Surgical evaluation			x
History & Physical	x	x	
Weight/BSA	x	x	
Vital Signs	x	x	
Performance Status	x	x	
Toxicity Assessment		x	
Laboratory Studies:			
CBC, Diff, Platelets	x		x
Serum Chemistries B	x		x
PT/INR C			x
CA 19-9, CEA	x		x
Research Blood Collection E	x I	x J	x K
Staging:			
CT (or MRI) F	x		x K
EUS (fiducials and elastography) G	x		x L
Tissue:			
Core Biopsy H	x		

Adjuvant mFOLFIRINOX and Post-Treatment Follow-Up:					
Tests & Observations	Day 1 of 1 st adjuvant cycle (within 12 weeks of surgery)	Day 3, 4, or 5 of each cycle	Day 1 of each subsequent cycle	Post-Treatment Follow-Up N	30-day follow-up
Scheduling Window (Days)	(±3)	(±3)	(±3)	(± 14)	(± 7)
History	X		X	X	X
Physical Exam	X		X	X	X
Weight/BSA	X		X	X	X
Vital Signs	X		X		
Performance Status	X		X	X	
Toxicity Assessment	X		X		
Neulasta Q		X			
Laboratory StudiesA:					
CBC, Diff, Platelets	X		X	X	
Serum Chemistries B	X		X	X	
CA 19-9, CEA	X			X	
Research Blood Collection E	X			X O	
Staging:					
CT (or MRI) F				X P	X
Tissue:					

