## 12. STATISTICAL METHODS

The primary endpoint of this phase II study is the R0 resection rate after neoadjuvant mFOLFIRINOX and SBRT in patients with BRPC.

In the largest reported series of patients with BRPC, 125 patients received pre-operative therapy consisting of 2 to 4 months of gemcitabine-based chemotherapy followed by fractionated chemoradiation. 41% of patients underwent a subsequent resection, and R0 resections were achieved in 94% of these patients, for an overall R0 resection rate of 39% for all patients initiating pre-operative therapy. Superior outcomes have been demonstrated with FOLFIRINOX compared to gemcitabine chemotherapy, and a local control benefit has been suggested with SBRT compared to fractionated chemoradiation. Thus, we propose an increase in the R0 resection rate from 40% in historical controls treated with standard gemcitabine-based chemotherapy and fractionated radiation prior to surgery to 65% with pre-operative FOLFIRINOX and SBRT.

A total of 28 patients will be enrolled in a Simon two-stage design with a provision for early stopping for lack of efficacy. The primary endpoint is the rate of achieving R0 resections. Patients needing to drop out of this study prior to surgery, for disease progression or treatment related toxicity, will be considered as failing to achieve the R0 resection rate. The null hypothesis is this rate is 40% based on both reported historical rates as well as our experience at Yale-New Haven Hospital. Under the alternative hypothesis, we will judge pre-operative modified FOLFIRINOX followed by SBRT effective if the R0 resection rate is 65% or higher. The optimal Simon two-stage design will terminate early if 5 or fewer of the first 13 patients fail to achieve an R0 resection. Otherwise we continue and enroll the remaining 15 patients for a total of 28. If 15 or more out of the full 28 achieve R0 resection then we reject the null hypothesis. This design has 90% power and significance level 0.1. The probability of stopping early under the null hypothesis is 57%.

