Secondary endpoints include radiographic response to neoadjuvant therapy, pathologic response to neoadjuvant therapy, rates of recurrence (local only, systemic only, and both local and systemic), progression free survival, overall survival, and rates of grade 3 or greater acute and late gastrointestinal toxicity. We will compare levels of KRAS mutation-associated circulating tumor DNA, CA19-9, and elastography measures with outcomes including R0 resection using logistic regression, and progression free survival and overall survival using proportional hazards regression. We will code IV contrast scans as binary and compare the before/after treatment within the same subject using the McNemar test for matched pairs. We have not powered this study for these secondary and exploratory measures. Future correlative biomarker studies will be studied using standard bioinformatics methods. Progression free survival, and overall survival will be estimated using Kaplan-Meier analysis. The Cox proportional hazards regression model will be used to determine if survival outcomes are associated with patient characteristics or treatment-related toxicities.

We anticipate accrual will be completed in two years based on the fact that approximately 40 resections for pancreatic adenocarcinoma are performed annually at Yale New Haven Hospital, of which around a third are for BRPC.

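### The post-SBRT research blood and CA19-9 are timed from surgery, so a patient who completes SBRT but is never operated on has no required post-SBRT value for a regression on R0 resection

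*Combined protocol and SAP*

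**What the plan says.** **Timing of the post-SBRT sample.** Three places time it from surgery:
- The ctDNA list in section 18.1: "After SBRT (within 4 weeks prior to surgery".
- The section 8 calendar column that holds CA19-9, research blood and CT: "Pre-operative (within 4 weeks prior to surgery".
- Footnote K to that column, attached to the research blood and the CT: "CT scan and plasma and serum samples will be done within 4 weeks prior to surgery".

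No other timing is given for a patient with no surgery date.

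**Use of the markers.** Objective 2.3.3 is "To correlate response of CA19-9 to pre-operative therapy with outcomes". Objective 2.3.1 asks the corresponding question for KRAS ctDNA. Section 12 relates ctDNA, CA19-9 and elastography "with outcomes including R0 resection using logistic regression" and names no marker time point. It also says that patients who leave before surgery for progression or toxicity "will be considered as failing to achieve the R0 resection rate".

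**Other draws.** Before surgery, ctDNA is also taken at diagnosis, at CT simulation and on SBRT fractions 3 and 5. CA19-9 is also taken at screening and before SBRT, but not during SBRT. Research blood is listed at progression, with no fixed time. CA19-9 is not.

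**Existing visit.** Section 6.3 states: "After completion of SBRT, patients will undergo re-evaluation for resection with a pancreas protocol CT scan".

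**The concern.** Whether the post-SBRT value exists depends largely on whether the patient is operated on, and being operated on is a precondition of R0 resection, the outcome to be modelled. A patient found unresectable after SBRT is an R0 failure, and under the written schedule no post-SBRT draw falls due.

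The rest of the schedule does not fill the gap:
- Sections 3.1 and 10 reserve surveillance for patients who complete study treatment without progression, and section 10 describes that treatment as running through surgery and post-operative chemotherapy.
- The 30-day follow-up column has a CT but no CA19-9 or research blood.
- The progression draw does not cover a patient who is unresectable without progression.
- For other patients, section 10 requires only survival follow-up.

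CA19-9 is the clearest case. Without surgery, its last scheduled value precedes SBRT, so it cannot show response to the whole pre-operative course. For ctDNA the gap is narrower: any value after fraction 5.

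An R0 regression that uses the post-SBRT value, or change from baseline to after SBRT, would compare R0 patients with operated non-R0 patients only. Later analysis cannot repair this, because the blood was never drawn.

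**Working it through.** **Inputs.** From section 12: N = 28; R0 rate 40% (null) and 65% (alternative); historical series of 125 patients, 41% resected, 94% of resections R0. From section 1.3: a multi-institutional mFOLFIRINOX trial with 22 treated, 15 resected and 14 R0.

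**Plan's own figure.** 0.41 × 0.94 = 0.385, which agrees with the stated 39%.

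**Where failures come from in the cited data.**
- Historical series: 125 × 0.41 = 51.3 resected; 51.3 × 0.94 = 48.2 R0; 3.1 resected but not R0; 73.8 not resected. Share of failures not resected: 73.8 / (73.8 + 3.1) = 96%.
- mFOLFIRINOX trial: 22 − 14 = 8 not R0, of whom 22 − 15 = 7 were not resected (88%).

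**Failures with a post-SBRT value if only resected patients are sampled.** Resected = 28 × R0 rate / 0.94. Failures = 28 × (1 − R0 rate). Failures with a value = resected − R0. The chance that no failure has a value is (1 − that number / 28)^28.

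| R0 rate | R0 | Resected | Failures | Failures with value | Lost | Chance of none |
|---|---|---|---|---|---|---|
| 40% | 11.2 | 11.9 | 16.8 | 0.7 | 96% | 0.485 |
| 65% | 18.2 | 19.4 | 9.8 | 1.2 | 88% | 0.305 |

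**Allowing for aborted operations.** A patient taken to surgery but not resected would have the sample. The documents give no rate, so 10% and 20% of operations are assumed. Taken to surgery = resected / (1 − aborted share); failures with a value = taken to surgery − R0.

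| R0 rate | 10% aborted | 20% aborted |
|---|---|---|
| 40% | 13.2 − 11.2 = 2.0 of 16.8 (12% kept) | 14.9 − 11.2 = 3.7 of 16.8 (22% kept) |
| 65% | 21.5 − 18.2 = 3.3 of 9.8 (34% kept) | 24.2 − 18.2 = 6.0 of 9.8 (61% kept) |

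**What retiming could recover.** Patients lost before SBRT ends cannot have a post-SBRT sample under any timing. The documents give no rate, so 0% to 30% of 28 is assumed. Failures with a value = failures − 28 × share lost.

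| Lost before end of SBRT | 40% R0 | 65% R0 |
|---|---|---|
| 0% | 16.8 | 9.8 |
| 10% | 14.0 | 7.0 |
| 20% | 11.2 | 4.2 |
| 30% | 8.4 | 1.4 |

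**The case against.** **The blood may travel with the CT.** Section 8 lists only one CT between SBRT and surgery, and footnote K puts that CT and the blood under one rule. Sections 3.1 and 6.3 use a post-SBRT CT to decide resectability. If this is the same scan, the surgery-based window has not cancelled the CT and need not cancel the blood. This reading is plausible, and some unresectable patients may be bled in practice. The text does not require it, however, and the window has no meaning for a patient without a surgery date.

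**A broader inference is not supported.** A reader might infer that the planned marker regressions as a whole lose nearly all their R0 failures. Section 12 names no time point. The baseline, CT-simulation or pre-SBRT, and SBRT-fraction samples do not depend on surgery, and ctDNA on fraction 5 falls on the last SBRT day. Regressions on those values keep their failures, except patients who leave before the visit.

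**The loss may be smaller.** Aborted operations keep some failures in. Patients who progress have a ctDNA draw listed, and the mFOLFIRINOX trial in section 1.3 attributes seven cases to progression. That draw has no fixed time and does not supply CA19-9, so it is not equivalent to a post-SBRT sample. Early losses also limit the gain: with 30% lost before SBRT ends and a 65% R0 rate, retiming yields 1.4 sampled failures against 1.2 as written.

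**These analyses are exploratory.** Section 12 says that they are unpowered. This stands and sets the severity.

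**Conclusion.** The concern holds for the post-SBRT value and for change over the whole neoadjuvant course (objectives 2.3.1 and 2.3.3). For those predictors, missingness depends on the outcome. If only resected patients are sampled and 94% of resections are R0, about one failure would have the value: 0.7 of 16.8 at 40% R0 and 1.2 of 9.8 at 65%. No logistic model can be reliably estimated from that. These are upper bounds on the loss. With an assumed 10–20% of operations aborted, 12–22% of failures keep a sample at 40% R0 and 34–61% at 65%.

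Regressions on earlier samples are unaffected, as are the primary endpoint and its decision rule. The point is minor. It is worth acting on because the remedy is cheap and a missed sample cannot be recovered.

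**What to change.** 1. In the section 8 calendar, footnote K and section 18.1, time the post-SBRT research blood and CA19-9 from the post-SBRT re-evaluation CT visit, for every patient who completes SBRT, whether or not surgery follows.
2. In section 12, name the marker time point or points used in the R0 regression.

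The cost is calendar and footnote wording, one sentence in section 12, and one blood draw (20–30 mL of research blood under footnote E, plus the CA19-9) at an existing visit for patients not operated on. The downside is that, where surgery is late, the sample may fall more than four weeks before resection. The change cannot supply a post-SBRT value for patients who leave before SBRT ends.
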